2.2 Study Design Overview

This is a randomized, double-blind, placebo-controlled Phase 2b study to assess the safety, tolerability, PK, PD, immunogenicity, and efficacy of ABBV-154 in subjects with moderately to severely active CD who had inadequate response to or were intolerant of prior biologics. The enrollment for subjects with prior adalimumab use is capped at approximately 30% of the total enrolled subjects. The study comprises 3 periods: a 12-Week Double-Blind Placebo-Controlled Induction Period, a 12-Week Double-Blind Re-Induction Period (for subjects considered to be clinical non-responders and endoscopic non-responders), and a 40-Week Double-Blind Placebo-Controlled Maintenance Period.

At the Baseline Visit of the Induction Period, approximately 265 subjects will be randomized in a 1:1:1:1 ratio into 4 ABBV-154 treatment groups or placebo:

- Induction Group 1: Loading dose of 150 mg IV at Week 0, followed by 80 mg subcutaneous (SC) at Week 2 and every other week (EOW);
- Induction Group 2: Loading dose of 300 mg IV at Week 0, followed by 230 mg SC at Week 2 and EOW;
- Induction Group 3: Loading dose of 600 mg IV at Week 0, followed by 530 mg SC at Week 2 and EOW;
- Induction Group 4: Loading dose of 600 mg IV at Week 0, followed by 530 mg SC at Weeks 4 and 8, and placebo at Weeks 2, 6, and 10; and

- Induction Group 5: Matching placebo (IV and SC).

At Week 12 of the Induction Period, subjects achieving clinical response, defined as a decrease in Crohn's Disease Activity Index (CDAI) ≥ 100 points from Baseline (CR100) AND/OR endoscopic response defined as a decrease in SES-CD $> 50\%$ from Baseline (or for subjects with isolated ileal disease and a Baseline SES-CD of 4, at least a 2-point reduction from Baseline) (per local read) will receive treatment in the 40-Week Maintenance Period as follows:

- Induction Group 1: Re-randomized in a 1:1 ratio to receive ABBV-154 80 mg SC EOW or matching placebo;
- Induction Groups 2 to 4: Re-randomized in a 1:1:1 ratio to receive ABBV-154 80 mg SC EOW, ABBV-154 230 mg SC EOW, or matching placebo;
- Induction Group 5: ABBV-154 80 mg SC EOW.

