At Week 12 of the Induction Period, subjects who are categorized as clinical non-responders and endoscopic non-responders (per local read) will be re-randomized into the Re-Induction Period. Subjects who receive Rescue Therapy, fail to complete glucocorticoid tapering by Week 6, or increase doses of or initiate treatment with aminosalicylates or immunomodulators in the Induction Period will be considered non-responders, regardless of clinical response or endoscopic response (per local read) per the definitions above at Week 12 and will be re-randomized in a 1:1 ratio into 2 ABBV-154 treatment groups in the 12-Week Re-Induction Period as follows:

- Re-Induction Group 1: Loading dose of 300 mg IV at Week 0, followed by 230 mg SC at Week 2 and EOW;
- Re-Induction Group 2: Loading dose of 600 mg IV at Week 0, followed by 530 mg SC at Week 2 and EOW.

Subjects who achieve clinical response AND/OR endoscopic response (per local read) at Week 12 of the Re-Induction Period will be re-randomized into the Maintenance Period as described above for subjects achieving clinical response AND/OR endoscopic response

(per local read) after Week 12 of the Induction Period. Subjects who do not achieve either clinical response or endoscopic response (per local read) after the Re-Induction Period will be discontinued and will have a follow-up visit scheduled 70 days after last study drug administration.

To determine endoscopic response status for re-randomization into the Maintenance Period, the SES-CD score per local read at Week 12 of the Induction/Re-Induction Period and the SES-CD score per central read at Baseline will be used. In the case of missing data where either clinical response or endoscopic response cannot be determined, subjects will be considered non-responders for the re-randomization criteria evaluation.

[figure not shown]
Subjects who have an inadequate response at or after Week 4 in the Maintenance Period will be eligible to receive Rescue Therapy with a single dose of ABBV-154 600 mg IV followed by ABBV-154 230 mg SC EOW. Subjects who have received rescue therapy with ABBV-154 for at least 4 weeks and who continue to demonstrate inadequate response may receive additional Rescue Therapy with oral glucocorticoids, aminosalicylates, or immunomodulators.

The last dose of study drug will be given at Week 38 of the Maintenance Period. A follow-up visit will be scheduled 70 days after the last study drug administration.

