The all ABBV-154 safety population (**SA-ALL154**) includes all subjects who received at least one dose of ABBV-154 in the Induction Period, or the Re-Induction Period, or the Maintenance Period.

The all ABBV-154 rescue safety population (**SA-RES**) includes all subjects who received at least one dose of ABBV-154 rescue therapy in the Maintenance Period.

The following safety populations are defined for safety analyses based on data from multiple study periods:

SA-IN2: all subjects who received at least one dose of ABBV-154 in both Induction Period and Re-Induction Period.

SA-INMN: all subjects who received at least one dose of ABBV-154 in either Induction Period or Re-Induction Period AND at least one dose of ABBV-154 in the Maintenance Period.

SA-IN2MN: all subjects who received at least one dose of ABBV-154 in the Induction Period AND at least one dose of ABBV-154 in the Re-Induction Period AND at least one dose of ABBV-154 in the Maintenance Period.

For the safety populations, subjects are assigned to a treatment group based on the "as treated" treatment group, regardless of the treatment randomized.

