Induction Period/Re-Induction Period + Maintenance Period ABBV-154 (SA-INMN population): TEAEs for "Induction Period/Re-Induction Period + Maintenance Period ABBV-154" (SA_INMN) are defined as events that begin either on or after the first dose of ABBV-154 in the Induction Period/Re-Induction Period and until (i) within 70 days after the last dose of study drug in the study, or (ii) initiation of ABBV-154 rescue therapy, whichever is earlier.

Induction Period + Re-Induction Period + Maintenance Period ABBV-154 (SA-IN2MN population): TEAEs for "Induction Period + Re-Induction Period + Maintenance Period ABBV-154" (SA-IN2MN) are defined as events that begin either on or after the first dose of ABBV-154 in the Induction Period and until (i) within 70 days after the last dose of study drug in the study, or (ii) initiation of ABBV-154 rescue therapy, whichever is earlier.

If an incomplete onset date was collected for an adverse event, the event will be assumed to be treatment-emergent unless there is other evidence that confirms that the event was not treatment-emergent (e.g., the event end date was prior to the study drug start date). The number and percentage of subjects experiencing treatment-emergent AEs will be summarized.

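### SA-INMN and SA-IN2MN admit Maintenance-placebo subjects only through a later rescue dose, then close the event window at rescue

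*SAP*

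**What the plan says.** **Entry.** SAP 4.0 places a subject in SA-INMN if ABBV-154 was received "in either Induction Period or Re-Induction Period AND at least one dose of ABBV-154 in the Maintenance Period". SA-IN2MN requires ABBV-154 in Induction plus "at least one dose of ABBV-154 in the Re-Induction Period AND at least one dose of ABBV-154 in the Maintenance Period". Neither definition limits the Maintenance dose to the assigned, blinded treatment.

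**Rescue.** Under SAP 2.2, Maintenance subjects with inadequate response from Week 4 are "eligible to receive Rescue Therapy with a single dose of ABBV-154 600 mg IV followed by ABBV-154 230 mg SC EOW". The SA-RES definition locates this treatment in the same period: that set "includes all subjects who received at least one dose of ABBV-154 rescue therapy in the Maintenance Period".

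**Placebo arm.** Responders from Induction Groups 2 to 4 are re-randomised to 80 mg, "ABBV-154 230 mg SC EOW, or matching placebo". Group 1 responders go to 80 mg or placebo. The Maintenance placebo arm therefore contains subjects who have already had ABBV-154.

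**Window.** For SA-INMN, SAP 10.2.1 counts events from the "first dose of ABBV-154 in the Induction Period/Re-Induction Period and until (i) within 70 days" onward. For both sets the end is the earlier of "i) within 70 days after the last dose of study drug in the study, or (ii) initiation of ABBV-154 rescue therapy, whichever is earlier". The summaries carry an ABBV-154 label.

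**Placebo exclusion.** SAP 10.2.1 (events) and SAP 10.2.4 (person-time) remove placebo periods for SA-ALL154. Neither section does so for SA-INMN or SA-IN2MN.

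**The concern.** Rescue is ABBV-154 given during Maintenance, so it satisfies the entry rule. A subject on active induction and then Maintenance placebo is outside both sets until the first rescue dose, and inside from then on. Because the window stops at rescue, that dose contributes nothing to what is counted. The subject contributes active induction time and then placebo time up to the flare.

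Placebo subjects who stay well never enter. Under Protocol 5.4, rescue needs a CDAI of at least 220, a rise of at least 70 points from Maintenance Baseline and a marker of inflammation. Membership thus depends on a later failure, and follow-up is cut at that failure. Protocol 6.1 treats worsening of a pre-existing condition as an adverse event, so the flare may itself be counted.

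At stake is how two combined-period tables read. Crohn's-worsening events could be too frequent for the exposure described, and events that depend on being on drug could be slightly diluted.

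**Working it through.** **1. The plan's own figure.** The SAP gives no size for these sets. The nearest figure is 40 per Maintenance group (SAP 2.4: 11% versus 37%, two-sided alpha 0.1, more than 80% power). Normal approximation:
- null SE = √(2 × 0.24 × 0.76 / 40) = 0.0955
- alternative SE = √((0.11 × 0.89 + 0.37 × 0.63) / 40) = 0.0910
- power = Φ((0.26 − 1.645 × 0.0955) / 0.0910) = 0.871

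The statement reproduces. Here 40 serves only as an illustrative arm size.

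**2. One subject under the literal rules.** With rescue at Maintenance Week w, the placebo share of the window is w/(12 + w) after 12 weeks of active treatment, and w/(24 + w) on the SA-IN2MN path.

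| Rescue week | SA-INMN (12 weeks active) | SA-IN2MN |
|---|---|---|
| 4 | 28/112 days = 25% | 28/196 = 14% |
| 12 | 84/168 = 50% | 84/252 = 33% |
| 24 | 168/252 = 67% | 168/336 = 50% |

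**3. Group illustration for SA-INMN.** Assumptions not given in the documents: 80 subjects on blinded ABBV-154, none rescued; 40 on placebo; 10% to 60% of the placebo subjects rescued, at Weeks 8 to 24.

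Share of the set made up of rescued placebo subjects:
- 10% rescued: 4/84 = 4.8%
- 20%: 8/88 = 9.1%
- 40%: 16/96 = 16.7%
- 60%: 24/104 = 23.1%

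Placebo share of window time. An unrescued active subject contributes 12 + 38 + 10 = 60 weeks, so 80 contribute 4,800:
- 40% rescued at Week 16: 16 × 16 = 256 placebo weeks; 256/(4,800 + 192 + 256) = 256/5,248 = 4.9%
- lowest (10%, Week 8): 32/(4,800 + 48 + 32) = 0.7%
- highest (60%, Week 24): 576/(4,800 + 288 + 576) = 10.2%

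**4. Allowing for the 70-day tail.** With the last active dose at Induction Week 10, the SAP's 70 days reach Maintenance Week 8 (Week 6 for Induction Group 4, last active at Week 8). In the 40%, Week 16 case, 16 × 8 = 128 placebo weeks lie beyond the tail: 128/5,248 = 2.4%.

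**5. Percentage with Crohn's worsening.** Assume 10% among the 80 active subjects (8/80).
- 40% rescued, every added subject with a recorded event: (8 + 16)/96 = 25%
- 40% rescued, added subjects at the same 10%: (8 + 1.6)/96 = 10%, no inflation
- ceiling across 10% to 60% rescued: (8 + 4)/84 = 14% to (8 + 24)/104 = 31%

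**6. Rate denominator.** SAP 10.2.4 sets exposure as last dose plus 70 days minus first dose, with no stop at rescue. If rescue doses to Week 38 count, exposure after 12 weeks of active induction is (12 + 38) × 7 + 70 = 420 days. The event window is 112 days for rescue at Week 4 (ratio 3.75) and 252 days at Week 24 (ratio 1.67). If last dose means the last blinded dose, say at Week 2 before rescue at Week 4, exposure is (12 + 2) × 7 + 70 = 168 days, still longer than 112. This pulls rates down, opposite to the flare effect.

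**The case against.** The strongest reply is that this is a drafting gap of small consequence. SAP 13.0 records that version 2.0 added rescue and cut these windows at its start, and lists no matching change to the entry rule. That suggests the sets were meant to describe non-rescue ABBV-154. SAP 10.1 introduces them as additional summaries after SA1, SA2, SA3, SA-RES and SA-ALL154. The pooled view, SA-ALL154, already removes placebo events and time. All of this stands and limits the weight of the point. It does not change what the entry rule says.

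As-treated assignment in SAP 4.0 might be thought to separate these subjects. It does not as written: no groups are defined for someone who moves from active drug to placebo to rescue, and grouping alters neither entry nor window.

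Three objections to the size also stand. Early placebo time falls within 70 days of the last active dose, so misattribution is clearest for later rescue, although the SA-ALL154 rule excludes all placebo time. Rescue is discretionary, and its 70-point rise is from Maintenance Baseline, so a subject may qualify while still below the study-entry CDAI; whether this is recorded as an adverse event is uncertain. The figure of 40 per group belongs to the efficacy analysis in ITT3, which omits subjects given ABBV-154 in both Induction and Re-Induction. SA-INMN includes those subjects and SA-IN2MN consists of them, so no group-level figure is offered for SA-IN2MN.

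A reader might infer that the trial's long-term safety profile is distorted, or that a jump from 10% to 25% is to be expected. The documents support neither: the membership and event windows of SA1, SA3, SA-RES and SA-ALL154 are untouched, and 25% is a ceiling under assumed inputs.

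**Conclusion.** The concern holds for SA-INMN and SA-IN2MN on the written rules. Subjects re-randomised to Maintenance placebo enter only by way of a flare that led to rescue, and what is then counted includes their placebo time but not the dose that admitted them. Selection for disease worsening is the main effect.

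Dilution of person-time is small: about 5% in the 40%, Week 16 case and roughly 1% to 10% over the assumed range. The change in the Crohn's-worsening percentage cannot be derived, because no rescue rate or recording rate is given; at 40% rescue it lies between none and a rise from 10% to 25%. These figures assume a 2:1 active-to-placebo split and no rescue among active subjects. The exposure rule in SAP 10.2.4 adds a separate mismatch between events and denominator. The point should be corrected, but it concerns secondary safety tables and not the efficacy conclusions.

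**What to change.** 1. In SAP 4.0, define SA-INMN and SA-IN2MN by at least one dose of blinded, non-rescue ABBV-154 in the Maintenance Period. SAP 6.0 and 10.2.1 already use the notion of blinded study drug. Rescue exposure stays in SA-RES and SA-ALL154, so none is lost. Extending only the SA-ALL154 placebo exclusion would remove the placebo time but leave the flare-selected subjects in the sets.
2. In SAP 10.2.4, end exposure for these two sets at initiation of rescue, so that the denominator matches the event window. This is also needed for active subjects who are rescued, whom the first change does not touch. The SA3 window likewise closes at rescue, so its denominator is worth checking in the same edit.

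The cost is one phrase per population and one sentence on exposure, with no new data. The downside is slightly smaller sets.

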5.0 Subject Disposition

A summary of subject accountability will be provided where the number of subjects in each of the following categories will be summarized by treatment group for each period separately, among the corresponding ITT population:

- Subjects enrolled (randomized) in the study;
- Subjects who took at least one dose of study drug;
- Subjects who completed protocol-specified treatment;
- Subjects who prematurely discontinued study drug;
- Subjects who withdrew from study.

Number and percentage of subjects who discontinued study drug and who withdrew from the study will be summarized by reason (primary reason and all reasons) and by treatment group for each period separately. Subjects with multiple reasons for premature discontinuation will be counted once in the calculation of the number and percentage of total discontinuations.

In addition, subjects who reported at least one of the protocol deviation categories ([Appendix A](#)) will be summarized for each treatment group.

6.0 Study Drug Duration and Compliance

For the safety populations (SA1, SA2 and SA3), duration of treatment will be summarized by each treatment group for each period. Duration of treatment is defined for each subject as last dose date of blinded study drug minus first dose date + 14. Duration of treatment

will be summarized for each treatment group using the number of subjects treated, mean, standard deviation, median, minimum, and maximum. In addition, the number and percentage of subjects in the following treatment duration intervals will be summarized.

Induction/Re-Induction Period: < 2 weeks [14 days], ≥ 2 weeks [14 days], ≥ 4 weeks [28 days], ≥ 8 weeks [56 days], and ≥ 12 weeks [84 days]

Maintenance Period: < 2 weeks [14 days], ≥ 2 weeks [14 days], ≥ 4 weeks [28 days], ≥ 8 weeks [56 days], ≥ 12 weeks [84 days], ≥ 24 weeks [168 days], ≥ 36 weeks [252 days], and ≥ 40 weeks [280 days]

Treatment compliance will be summarized by treatment group for each period for the safety population. Treatment compliance is defined as the number of infusions/injections actually taken divided by the number of infusions/injections that should have been taken. Percent compliance will be summarized.

7.0 Demographics, Baseline Characteristics, Medical History, and Prior/Concomitant Medications

Demographics, baseline or disease characteristics, medical history, and prior and concomitant medications will be summarized overall and by treatment group, and overall for each of the ITT1/ITT2/ITT3/ITT3-RN/ITT3-NRN population. Categorical variables will be summarized with the number and percentage of subjects; percentages will be calculated based on the number of non-missing observations. Continuous variables will be summarized with descriptive statistics (number of non-missing observations, mean, standard deviation, median, minimum, and maximum).

7.1 Demographics and Baseline Characteristics

Demographic/vital Signs

- Sex (Male, Female)
- Age (Years)
- Age Category (≥ 18 years - < 40 years, ≥ 40 years - < 65 years, ≥ 65 years)

- Ethnicity (Hispanic/Latino, Non-Hispanic/Latino)
- Race category (White, Black or African American, American Indian or Alaska Native, Native Hawaiian or Other Pacific Islander, Asian, Multiple)
- Geographic Region category (US, ex-US)
- Geographic Region category (Asia, Eastern Europe, Western Europe, North America, South/Central America, Other)
- Tobacco/Nicotine Use (currently smokes, ex-smoker, never smoked, unknown)
- Alcohol use (current drinker, former drinker, non-drinker, unknown)
- Body weight (kg) – overall and by sex
- Body Mass Index (BMI, kg/m²)
- BMI category
 - [< 18 kg/m²]
 - [≥ 18 and < 25 kg/m²]
 - [≥ 25 and < 30 kg/m²]
 - [≥ 30 kg/m²]

Patient Reported Outcome Questionnaires at Baseline

- IBDQ total and domain scores
- FACIT-F total score
- SF-36 - 8 domain scores, PCS and MCS
- PGIS-CD+

Other Baseline Characteristics

- CDAI
- Average Daily very soft or liquid SF
- Average Daily AP score
- SES-CD
- SES-CD category (< 15 , ≥ 15)

- Crohn's disease Duration (years)
- Crohn's disease Duration category (≤ 5 years, > 5 years)
- hs-CRP (mg/L)
- hs-CRP category (< 5 , ≥ 5 mg/L)
- FCP ($\mu\text{g/g}$)
- FCP category (≤ 250 $\mu\text{g/g}$, > 250 $\mu\text{g/g}$)
- CD Location Per SES-CD (ileal, ileocolonic, colonic; [Appendix F](#))

Prior and Concomitant Treatment use

- Baseline CD-related glucocorticoid use (yes, no)
- Baseline CD-related immunomodulator use (yes, no)
- Baseline CD-related aminosalicylates use (yes, no)
- Prior inadequate response and/or intolerance to biologics
 - Number of prior biologics with inadequate response and/or intolerance (≤ 1 , 2 , ≥ 3)
 - Prior inadequate response and/or intolerance to an anti-TNF agent (yes, no)
 - Inadequate response to an anti-TNF agent (yes, no)
 - Intolerance to an anti-TNF agent (yes, no)
 - Inadequate response to adalimumab (yes, no)
 - Prior inadequate response and/or intolerance to vedolizumab/natalizumab (yes, no)
 - Prior inadequate response and/or intolerance to ustekinumab (yes, no)

In addition, clinical tests at baseline such as TB test, pregnancy test and electrocardiogram assessment will be summarized. Crohn's disease history (Montreal classification) and Crohn's disease surgical history will be summarized separately as well.

7.2 Medical History

Medical history data will be coded using the Medical Dictionary for Regulatory Activities (MedDRA). The actual version of the MedDRA coding dictionary will be noted in the statistical tables and clinical study report. The number and percentage of subjects in each medical history category [by MedDRA system organ class (SOC) and preferred term (PT)] will be summarized overall and by treatment group. The SOC will be presented in alphabetical order, and the preferred terms will be presented in alphabetical order within each SOC. Subjects reporting more than one condition/diagnosis will be counted only once in each row (SOC or PT).

7.3 Prior and Concomitant Medications

Prior and concomitant medications will be summarized by generic name (ITT1 population for prior medications; ITT1, ITT2 and ITT3/ITT3-RN/ITT3-NRN populations for concomitant medications). A prior medication is defined as any medication taken prior to the date of the first dose of study drug in the Induction Period.

A concomitant medication for the Induction Period is defined as any medication other than study drug that (1) was started prior to the first dose study drug in the Induction Period and continued to be taken after the first dose of study drug in the Induction Period, or (2) was started after the first dose of study drug in the Induction Period, but (i) prior to the first dose of study drug in the Re-Induction Period (if applicable), or (ii) prior to the first dose of study drug in the Maintenance Period (if applicable), or (iii) within the last dose in the Induction Period + 14 days, whichever is earlier.

A concomitant medication for the Re-Induction Period is defined as any medication other than study drug that (1) was started prior to the first dose study drug in the Re-Induction Period and continued to be taken after the first dose of study drug in the Re-Induction Period, or (2) was started after the first dose of study drug in the Re-Induction Period, but (i) prior to the first dose of study drug in the Maintenance Period (if applicable), or (iii) within the last dose in the Re-Induction Period + 14 days, whichever is earlier.

A concomitant medication for the Maintenance Period is defined as any medication other than study drug that (1) was started prior to the first dose study drug in the Maintenance Period and continued to be taken after the first dose of study drug in the Maintenance Period, or (2) was started after the first dose of study drug in the Maintenance Period, but (i) within the last dose in the Maintenance Period + 14 days, or (ii) prior to initiation of ABBV-154 rescue therapy, whichever is earlier.

The number and percentage of subjects taking medications will be summarized by generic drug name based on the World Health Organization (WHO) Drug Dictionary for both prior and concomitant medications.

